The Pfizer-BioNTech original monovalent COVID-19 Vaccine was previously authorized for booster vaccination as (1) a single booster dose in individuals aged 5 to 11 years, (2) a first booster dose in individuals aged 12 years and older, (3) a second booster dose in immunocompromised individuals aged 12 years and older, and (4) a second booster dose in individuals aged 50 years and older (FDA, 2023). A chronological history of FDA EUA of Pfizer-BioNTech original monovalent COVID-19 Vaccine for booster vaccination is summarized below.

• On 22 September 2021, the FDA authorized emergency use of a single booster dose of the Pfizer-BioNTech original monovalent COVID-19 Vaccine to be administered at least 6 months after completion of a primary series of Pfizer-BioNTech original monovalent COVID-19 Vaccine in individuals aged 65 years and older; individuals aged 18 through 64 years at high risk of severe COVID-19; and individuals aged 18 through 64 years

PFIZER CONFIDENTIAL

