7. RESEARCH QUESTION AND OBJECTIVES

Research questions

Among the general population, immunocompromised individuals, pregnant women, and individuals with a history of COVID-19:

- 1. What is the incidence of safety events of interest, including myocarditis/pericarditis, among individuals receiving at least 1 dose in a primary series¹ of Pfizer-BioNTech original monovalent COVID-19 Vaccine compared with that among individuals who have not received any vaccination for COVID-19 in the US?
- 2. In individuals aged 5 years and older who have received the first and second dose in a primary series¹ of Pfizer-BioNTech original monovalent COVID-19 Vaccine, what is the incidence of safety events of interest, including myocarditis/pericarditis, among individuals vaccinated with a third dose (either as an additional dose in a primary series or as a booster dose) of Pfizer-BioNTech original monovalent COVID-19 Vaccine compared with that among individuals who have not received a third dose of any COVID-19 vaccine in the US?
- 3. What is the prevalence of birth outcomes of interest (including major congenital malformations and small size for gestational age) in infants born to pregnant women who were exposed to Pfizer-BioNTech original monovalent COVID-19 Vaccine as compared with that among infants born to pregnant women who were not exposed to any COVID-19 vaccine in the US?

Primary study objectives

Among the overall study population and subgroups of pregnant women, immunocompromised individuals, and individuals with a history of COVID-19:

- 1. In individuals aged 5 years and older: To estimate the RR of safety events of interest (including myocarditis/pericarditis) following receipt of a first, second, or third (if received within 2 months of the second dose) dose in a primary series¹ of Pfizer-BioNTech original monovalent COVID-19 Vaccine compared with that among individuals with no receipt of any COVID-19 vaccine
- 2. In individuals aged 6 months through 4 years: To estimate the RR of safety events of interest (including myocarditis/pericarditis) following receipt of a first, second, or third dose in a primary series¹ of Pfizer-BioNTech original monovalent COVID-19 Vaccine compared that among individuals with no receipt of any COVID-19 vaccine

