Dose 2 exposed	Record of a second dose in the primary series of Pfizer-BioNTech original monovalent COVID-19 Vaccine	Date of second dose	Record of COVID- 19 vaccine other than Pfizer- BioNTech original monovalent COVID-19 Vaccine before the index date
Dose 3 exposed ^a	For individuals aged 6 months through 4 years: record of a third dose in the primary series of Pfizer-BioNTech original monovalent COVID-19 Vaccine For individuals aged 5 years or older: record of a third dose in the primary series of Pfizer-BioNTech original monovalent COVID-19 Vaccine within 2 months after the second dose	Date of third dose	Record of COVID- 19 vaccine other than Pfizer- BioNTech original monovalent COVID-19 Vaccine before the index date
Dose 1 unexposed	No record of any COVID-19 vaccine as of the index date (i.e., cohort entry) and matched individually to individuals in the dose 1 exposed cohort on time– specific propensity score, age, sex, and state (if feasible, or broader geographic region if not feasible)	Randomly selected date in a period within close temporal proximity to the date of first dose in corresponding exposed individuals (e.g., within the same calendar month)	Record of any COVID-19 vaccine before the index date

Table 1.Cohort definitions for primary series analysis of the general population,
immunocompromised individuals, and individuals with a history of
COVID-19

Cohort	Inclusion criteria	Index date	Exclusion criteria
Dose 2 unexposed	No record of any COVID -19 vaccine as of the index date (i.e., cohort entry) and matched individually to individuals in the dose 2 exposed cohort on time– specific propensity score, age, sex, and state (if feasible, or broader geographic region if not feasible)	Randomly selected date in a period within close temporal proximity to the date of second dose in corresponding exposed individuals (e.g., within the same calendar month)	Record of any COVID-19 vaccine before the index date
Dose 3 unexposed ^a	No record of any COVID-19 vaccine as of the index date (i.e., cohort entry) and matched individually to individuals in the dose 3 exposed cohort on time– specific propensity score, age, sex, and state (if feasible, or broader geographic region if not feasible)	Randomly selected date in a period within close temporal proximity to the date of third dose in corresponding exposed individuals (e.g., within the same calendar month)	Record of any COVID-19 vaccine before the index date

COVID-19 = coronavirus disease 2019.

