Table 3.	Eligible populations and exposure windows for analyses of pregnant
	women

Event	Eligible population	Exposure window
General safety events ^a	All eligible pregnancies	4 weeks before estimated pregnancy start to end of pregnancy
Pregnancy safety outco	omes	
Spontaneous abortion	All eligible pregnancies	4 weeks before estimated pregnancy start to end of pregnancy or 19-6/7 weeks of gestation, whichever is earlier
Stillbirth	All eligible pregnancies	4 weeks before estimated pregnancy start to end of pregnancy
Preterm birth	All eligible pregnancies	4 weeks before estimated pregnancy start to end of pregnancy or 36-6/7 weeks of gestation, whichever is earlier
Major congenital malformations	Singleton live deliveries with linkage to infant data available	4 weeks before estimated pregnancy start to 13-6/7 weeks of gestation (end of first trimester)
Small size for gestational age	Singleton live deliveries with linkage to infant data available	4 weeks before estimated pregnancy start to end of pregnancy

a. Safety events of interest listed in Table 8 in Section 8.3.2.1.

Analyses of major congenital malformations and small size for gestational age will require pregnancies to be linked to infants who have health plan enrollment from birth until age 3 months (or from birth until death if the infant dies before age 3 months). Where available, the Sentinel mother-infant linkage table (see Section 8.4) included in the most recently approved ETL (Extract, Transform, Load) at the time of the data extraction will be used for this study. Mother-infant linkage algorithms differ by data source and may use subscriber identification numbers and/or names and addresses; these algorithms will be described in the SAP.

8.2.3.1. Primary series analyses of general safety events, spontaneous abortion, stillbirth, and preterm birth in pregnant women

Cohort definitions for primary series analyses of general safety events, spontaneous abortion, stillbirth, and preterm birth are presented in Table 4. The primary series analysis will include dose 1, dose 2, and dose 3 if a third dose is received within 2 months of the second dose. Similar to the analytic approach in the general population, separate cohorts will be formed for each dose of Pfizer-BioNTech original monovalent COVID-19 Vaccine to assess these

PFIZER CONFIDENTIAL

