CT24-WI-GL02-RF02 3.0 Non-Interventional Study Protocol Template For Secondary Data Collection Study 20-May-2021 Page 55 of 120 events. In addition to meeting criteria described in Table 2, individuals must also meet criteria in Table 4 to be included in the exposed/unexposed cohorts.

Cohort	Inclusion criteria	Index date	Exclusion criteria
Dose 1 exposed	Record of a first dose of Pfizer- BioNTech original monovalent COVID-19 Vaccine during the exposure window ^b	Date of first dose	Record of any COVID-19 vaccine other than Pfizer- BioNTech original monovalent COVID-19 Vaccine before the index date (or during the exposure window before the index date in analyses of spontaneous abortion, stillbirth, and preterm birth)
Dose 2 exposed	 Record of a second dose of Pfizer-BioNTech original monovalent COVID-19 Vaccine during the exposure window For analysis of general safety events, the first dose is not required to have been administered during the exposure window For analysis of spontaneous abortion, stillbirth, and preterm birth, if the first dose is administered before the exposure window, the pregnancy will NOT be eligible for dose 1 exposed cohort analysis but will be eligible for dose 2 exposed cohort analysis 	Date of second dose	Record of any COVID-19 vaccine other than Pfizer- BioNTech original monovalent COVID-19 Vaccine before the index date (or during the exposure window before the index date in analyses of spontaneous abortion, stillbirth, and preterm birth)

Table 4.Cohort definitions for primary series analyses of general safety events,
spontaneous abortion, stillbirth, and preterm birth in pregnant women^a

Table 4.	Cohort definitions for primary series analyses of general safety events,
	spontaneous abortion, stillbirth, and preterm birth in pregnant women ^a

Cohort	Inclusion criteria	Index date	Exclusion criteria

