Dose 3 exposed	 Record of a third dose (either as an additional dose in a primary series or as a booster dose) of Pfizer-BioNTech original monovalent COVID-19 Vaccine during the exposure window For analyses of general safety events, the first and second dose are not required to have been administered during the exposure window For analyses of spontaneous abortion, stillbirth, and preterm birth, the first and/or second doses may be administered before the exposure window but only the third dose will be eligible for the dose 3 cohort 	Date of third dose	Record of any COVID-19 vaccine other than Pfizer- BioNTech original monovalent COVID-19 Vaccine before the index date (or during the exposure window before the index date in analyses of spontaneous abortion, stillbirth, and preterm birth)
Dose 1 unexposed	 No record of any COVID-19 vaccine as of the index date (or no record of any COVID-19 vaccine during the exposure window before the index date in analyses of spontaneous abortion, stillbirth, and preterm birth) Individually matched to women in dose 1 cohort on maternal age and pregnancy start date and US state (if feasible) 	Equivalent of the gestational age (in days) at the time of the of the dose 1 exposed individual's index datec	Record of any COVID-19 vaccine as of the index date (or during the exposure window before the index date in analyses of spontaneous abortion, stillbirth, and preterm birth)
Dose 2 unexposed	Same criteria as the dose 1 unexposed cohort, but matched individually to women in the dose 2 exposed cohort	Equivalent of the gestational age (in days) at the time of the dose 2 exposed individual's index date ^c	Same criteria as those for the dose 1 unexposed cohort

Table 4.	Cohort definitions for primary series analyses of general safety events,
	spontaneous abortion, stillbirth, and preterm birth in pregnant women ^a

Cohort	Inclusion criteria	Index date	Exclusion criteria
Dose 3 unexposed	Same criteria as those for the dose 1 unexposed cohort, but matched individually to women in the dose 3 exposed cohort	Equivalent of the gestational age (in days) at the time of the dose 3 exposed individual's index date ^c	Same criteria as those for the dose 1 unexposed cohort

COVID-19 = coronavirus disease 2019; FU = follow-up.

a. Safety events of interest listed in Table 8 in Section 8.3.2.1.

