Eligibility criteria for third dose analyses of general safety events, spontaneous abortion, stillbirth, and preterm birth in pregnant women are described in Table 5. To be eligible, women must have received 2 doses of the Pfizer-BioNTech original monovalent COVID-19 Vaccine. They must be pregnant for at least 1 day after dose 2 and be continuously enrolled in their health plan from 12 months before the index date (as defined in Table 5) until the end of pregnancy. Depending on whether data on vaccine dose number are recorded in the data sources, additional enrollment may be required from the beginning of authorization of the Pfizer-BioNTech original monovalent COVID-19 Vaccine (i.e., 11 December 2020) to enable dose number identification. The feasibility of determining dose number based on vaccine codes will be confirmed during the monitoring phase of the study, and all eligibility criteria will be fully documented in the SAP.

PFIZER CONFIDENTIAL

CT24-WI-GL02-RF02 3.0 Non-Interventional Study Protocol Template For Secondary Data Collection Study 20-May-2021 Page 58 of 120 The same exposure windows and eligible populations will be used as for the analysis of the doses in the primary series (as defined in Table 3). Only third doses of Pfizer-BioNTech original monovalent COVID-19 Vaccine (received as an additional dose in a primary series or as a booster dose) administered during the exposure windows and more than 2 months after the second dose will be considered for inclusion in the dose 3 exposed cohort. Women who receive a third dose after their pregnancy ends will not contribute person-time to the dose 3 exposed cohort but may contribute unexposed person-time to the dose 3 unexposed cohort.

Table 5.	Cohort definitions for third dose analyses of general safety events ^a ,
	spontaneous abortion, stillbirth, and preterm birth in pregnant women

Cohort	Inclusion criteria	Index date	Exclusion criteria
General safe	ty events		
Dose 3 exposed	 Receipt of a third dose of Pfizer-BioNTech original monovalent COVID-19 Vaccine (either as an additional dose in a primary series or as a booster dose) during the exposure window, more than 2 months after the second dose Note that the first 2 doses are not required to have been received during the exposure window 	• Date of third dose of Pfizer- BioNTech original monovalent COVID-19 Vaccine	Receipt of any COVID-19 vaccine other than Pfizer- BioNTech original monovalent COVID-19 Vaccine before the index date

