8.7.2.3.2. Pregnant women

8.7.2.3.2.1. Analysis of general safety events, spontaneous abortion, stillbirth, and preterm birth following a primary series in pregnant women

The risk of general safety events, spontaneous abortion, stillbirth, and preterm birth will be compared among women who have received at least the first dose in a primary series of Pfizer-BioNTech original monovalent COVID-19 Vaccine versus those among pregnant women who have not received any COVID-19 vaccine during a concurrent time period. These analyses will include dose 1 and dose 2, as well as dose 3 if a third dose is received within 2 months of the second dose.

To minimize confounding by seasonality and maternal age, within the data from each data research partner, exposed pregnant women will be matched to unexposed pregnant women on estimated pregnancy start date (+/- 14 days), state (if feasible, or broader geographic region if not feasible), and maternal age. Propensity scores will be estimated within the matched population and incorporated into regression analysis for exposure-outcome associations (e.g., through weighting or stratification) to address confounding by other variables. The matching and propensity score estimation process will be done first for the overall population of pregnant women. The process will then be repeated for the subsets of pregnant women eligible for analyses of the different safety events of interest (e.g., pregnancies surviving beyond 20 completed weeks of pregnancy for analysis of stillbirth; live births for analysis of preterm birth).

The steps for matching and propensity score analysis are as follows.

a. Unexposed individuals will be matched on estimated pregnancy start date, state (or broader geographic region, as feasible), and maternal age to exposed individuals within each data research partner (in a ratio of at least 1:1). The matching will be done separately for the dose 1 exposed cohort, for the dose 2 exposed cohort, and for the dose 3 exposed cohort.

PFIZER CONFIDENTIAL

CT24-WI-GL02-RF02 3.0 Non-Interventional Study Protocol Template For Secondary Data Collection Study 20-May-2021 Page 94 of 120 An individual may be selected for each unexposed cohort (i.e., dose 1 unexposed, dose 2 unexposed cohort, or dose 3 unexposed cohort) only once. However, if an individual becomes vaccinated after being selected as an unexposed match, they may be eligible for the exposed cohort(s).

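### In pregnant women, the Table 4 dose 3 exposed row has no interval limit and admits boosters, contradicting the protocol's own 2-month limit for primary-series third doses

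*Protocol*

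**What the plan says.** Two definitions of a primary-series third dose in pregnant women stand in the current text.

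**With the 2-month limit.**
- Primary objective 1 (Section 7), which covers pregnant women as a subgroup, admits a "third (if received within 2 months of the second dose".
- The paragraph introducing Table 4 (8.2.3.1) includes "dose 3 if a third dose is received within 2 months of the second dose".
- The pregnancy analysis section (8.7.2.3.2.1) repeats it: "as well as dose 3 if a third dose is received within 2 months of the second dose".
- Section 8.1 and Table 7 footnote c make the limit exclusive: at age 5 and over, later third doses stay out of the primary-series analysis.
- The parallel general-population row in Table 1 has it too: "record of a third dose in the primary series of Pfizer-BioNTech original monovalent COVID-19 Vaccine within 2 months after the second dose".

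**Without it.** The Table 4 dose 3 exposed row reads "Record of a third dose (either as an additional dose in a primary series or as a booster dose) of Pfizer-BioNTech original monovalent", followed by the product name and the exposure-window condition. No interval from dose 2 is given.

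The lead-in to Table 4 adds: "In addition to meeting criteria described in Table 2, individuals must also meet criteria in Table 4". Table 2 is the cohort table for third doses received more than 2 months after dose 2.

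Late third doses in pregnancy have their own analysis. Under 8.2.3.2 and Table 5, only those "administered during the exposure windows and more than 2 months after the second dose will be considered for inclusion in the dose 3 exposed cohort", with two-dose women as comparators.

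**The concern.** Section 8.2.3.1 presents Table 4 as its cohort definitions, so it is the natural place to code from. Coded as written, the dose 3 row brings boosters into a cohort that primary objective 1 confines to early third doses. The dose 3 relative risk in pregnant women would then describe, at least in part, a different exposure from the one stated.

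The comparator changes as well. Table 5 sets late third doses against women who already had two doses. Table 4 sets them against women with no COVID-19 vaccine as of the index date (general safety events), or with none in the exposure window before that date (spontaneous abortion, stillbirth, preterm birth). Under Section 8.7.2.2, if the dose-specific estimates look similar, the dose 3 data are pooled into the estimate for at least one dose, and the boosters would go with them.

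This is not detail left for the SAP. The protocol gives incompatible cohort definitions for a primary objective, and an SAP author cannot follow all of them.

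**Working it through.** There is no stated figure to reproduce. The check sets the passages side by side, then asks how much could be affected.

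**1. Third-dose definitions compared**

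| Place | Interval after dose 2 | Boosters named | Comparator |
|---|---|---|---|
| Objective 1; 8.1; 8.2.3.1 text; Table 7 note c; 8.7.2.3.2.1 | within 2 months | no | no COVID-19 vaccine |
| Table 1, dose 3 (age 5+) | within 2 months | no | no vaccine as of index |
| Table 4, dose 3 | none stated | yes | no vaccine as of index, or none in window before index |
| Table 2, dose 3 | more than 2 months | yes | two prior doses |
| Table 5, dose 3 | more than 2 months | yes | two prior doses |

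**2. Can an on-schedule booster meet the limit?** Section 6 gives the first booster authorization as "at least 6 months after completion of a primary series", and later at least 5 months. At 30.44 days per month, 2 months is about 61 days, 5 months about 152 and 6 months about 183. The ranges do not overlap, so the limit removes every booster given at or after the authorized interval.

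**3. Can the Table 2 cross-reference be followed?**
- Exposed women: the section text (2 months or less) and Table 2 (more than 2 months) together leave nobody.
- Comparators, general safety events: two prior doses (Table 2) and no vaccine as of the index date (Table 4) also leave nobody.
- Comparators, pregnancy outcomes: two doses before the window and none in it is possible, so this set is not empty.
- Table 2 has no dose 1 or dose 2 rows, although Table 4 does.

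**4. Do the same doses also enter Table 5?** For general safety events, yes: Table 5 does not require the first two doses in the window. For spontaneous abortion, stillbirth and preterm birth it does. Counting from estimated pregnancy start, the spontaneous abortion window runs from day −28 to 19 × 7 + 6 = day 139. With doses 3 weeks apart (Section 6), dose 2 falls no earlier than −28 + 21 = day −7, and a booster at 5 months no earlier than −7 + 152 = day 145. That is past day 139, so no on-schedule booster enters Table 5 for this outcome. The stillbirth and preterm birth windows run later, so overlap there is possible but only for women with both earlier doses in the window. Table 4 lets those doses precede the window, so it would take in boosters that Table 5 excludes.

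**5. How large could the booster share be?** The documents give no counts. Footnote 1 to the objectives restricts a three-dose primary series at age 5 and over to immunocompromised individuals, while Section 6 records booster authorization for all adults. Among boosters plus within-2-month third doses:

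share = (1 − p)b / [(1 − p)b + pt]

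All inputs are assumptions: p, immunocompromised share of two-dose women, 2–10%; t, share of these with a third dose within 2 months, 10–75%; b, booster uptake in the others during the window, 5–50%.

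- p = 3%, t = 25%, b = 20%: 0.194 / (0.194 + 0.0075) = 96%
- p = 7%, t = 50%, b = 20%: 0.186 / (0.186 + 0.035) = 84%
- p = 10%, t = 75%, b = 5%: 0.045 / (0.045 + 0.075) = 38%

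Over a grid of 100 combinations the share runs from 38% to 99.6% and exceeds half in 97. The share is 50% when b = pt/(1 − p): 0.8% for p = 3%, t = 25%, and 8.3% for p = 10%, t = 75%.

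**The case against.** The best defence is that the limit is stated often enough to govern the table. Section 8.1 and Table 7 footnote c are exclusive, the paragraph introducing Table 4 repeats the rule, and the table is titled as a primary-series analysis. Read with these, the row admits no late third dose and the pooling worry disappears. Section 8.3.1 expects most vaccination codes to carry no dose number, so the booster wording might only mean that the label on the dose is ignored. If the cross-reference was meant for Table 1, the limit would already apply. On this view the defect is editorial.

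Part of this stands: the intended design can be recovered from the rest of the protocol. But reading the booster wording as indifference to labels is a guess. Under the limit that wording has almost no content, since an on-schedule booster cannot qualify. The cross-reference as printed points to the opposite interval.

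A reader might also infer three stronger claims, which the documents do not support:
- *Comparators are never-vaccinated women throughout.* This is exact only for general safety events. For the three pregnancy outcomes, comparators may have been vaccinated before the window.
- *Every booster in pregnancy is analysed twice.* This fails for the pregnancy outcomes, because Table 5 requires the first two doses in the window.
- *The cohort would be mostly boosters.* This is plausible but rests wholly on assumed inputs.

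**Conclusion.** The contradiction is real and lies in the current text. The Table 4 dose 3 exposed row conflicts with six other places in the protocol, and the cross-reference to Table 2 cannot be met together with the primary-series definition. The row as written admits boosters to a primary-objective cohort. For general safety events the same doses would also be analysed under Table 5 against a different comparator.

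The effect depends on how the table is coded. If the 2-month rule is applied over the row, there is none. If the row is taken literally, the booster share is unknown but could be large (38% to 99.6% under the assumed ranges), because a third primary-series dose at age 5 and over is confined to immunocompromised individuals. The contradiction does not depend on those assumptions. It should be resolved before the cohorts are coded.

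**What to change.** - **Table 4, dose 3 exposed row:** add the limit of 2 months after the second dose, as the Table 1 row does, keep the exposure-window condition, and delete the words that admit a booster. Later third doses are then analysed only under Table 5.
- **Lead-in to Table 4:** correct the reference to Table 2. The documents do not settle what was meant. Table 1 is the primary-series cohort table and carries the limit; Table 3 gives the eligible populations and exposure windows for pregnant women. The sponsor should confirm. If Table 1 is chosen, its footnote a counts the 2 months from the first dose while its row counts from the second, so that needs aligning too.
- **Table 4 footnote b:** for the pregnancy outcomes it lets a second dose in the window count in the dose 1 cohort and extends similar rules to third doses, while the table rows keep each dose in its own cohort. State one rule.

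The cost is wording only, with no new data. The pregnant primary-series dose 3 cohort may become much smaller and its estimate less precise, but it would match the stated objective.
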